2.1. Overview

First Episode Psychosis (FEP) as a Public Health Priority:

An FEP is one of the most frightening and disabling experiences from which a young person can suffer. Onset occurs in nearly all cases in youth and emerging adults (YEA), a crucial transition time, when major developmental milestones (high school graduation, first intimate relationship, maturation of executive function) occur^{1,2,3}. An FEP typically occurs in the context of diagnoses of schizophrenia, schizoaffective disorder, psychotic disorder NOS, substance-induced psychosis, and psychotic bipolar disorder, which when taken together are the most disabling disorders (among all medical illnesses) for YEA in OECD countries (causing over 10% of the total disability adjusted life years (DALYs) in this population⁴). Recent evidence from the U.S. shows the lethality of an FEP: associated mortality rates are 24 times greater in the 12 months after diagnosis compared to the general population⁵. Suicide, the second leading cause of death among youth in Canada, remains much higher in early psychosis than in the general population. Even after accounting for suicide, persons suffering from these illnesses have a shortened lifespan that is attributed to early mortality, primarily due to downward socioeconomic drift and poorly treated medical disorders, a reflection of the gross inequity experienced by those with an FEP in relation to the general population^{6,7,8}.

Early Psychosis Intervention (EPI) Programs: Life-Saving, but Lack of High Quality Care:

The emergence of EPI programs has provided tremendous hope by providing early intervention^{9,10,11}. Work by our team, recently published in the American Journal of Psychiatry¹², shows that youth who access an EPI program in Ontario, Canada receive faster psychiatric follow-up, better coordination of care between inpatient and outpatient services, reduced burden on the emergency department, and reduced all-cause mortality. Our system-level data support EPI programs as a critical life-saving intervention. Internationally, EPI has demonstrated significant benefits compared to treatment as usual with respect to engagement, service utilization, and suicide^{9,13,14,15}.

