3.2. Hypotheses

1. Following the implementation of NAVIGATE, program fidelity to the Ontario EPI standard will improve.
2. Compared to patients not receiving NAVIGATE, those who receive NAVIGATE through this implementation study will have fewer days in hospital, fewer ED visits, fewer suicide attempts, lower mortality, and lower costs.
3. Improvements in functioning and symptoms will be comparable to the RAISE study; improvement may be influenced by demographic, socio-economic, geographic, and clinical factors.
4. Our engagement approach will demonstrate that we used the full range of patient engagement based on objectively assessed engagement metrics.

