Staff interview (value and feasibility)*	CFIR adapted					•
Implementation outcomes (staff capacity)						
Staff survey (knowledge and skills)	ECHO survey	•			•	•

* includes perceptions of ECHO support

System Level Outcomes + Analytic Plan (Objective 2):

Data Sources: The primary data collected for patients of the NAVIGATE protocol will be linked deterministically to data sources held at the Institute for Clinical Evaluative Sciences (ICES) via their unique health card number. The patient-level outcomes are enhanced by routine system-level outcome measurement and the capacity to compare outcomes among NAVIGATE subjects with two control populations: 1) FEP subjects in Ontario who are not part of the NAVIGATE trial but are receiving EPI services; and 2) FEP patients with no EPI contact. Only NAVIGATE patients who have consented will have their program-level data linked to ICES. The following ICES data sources will be used: the Ontario Health Insurance Plan (OHIP) which covers data for physician billings; the Canadian Institute for Health Information Discharge Abstract Database (CIHI-DAD) which covers all hospitalizations; the Ontario Mental Health Reporting System (OMHRS), covering adult mental health hospitalizations; the National Ambulatory Care Reporting System (NACRS) for emergency department (ED) visits; the Ontario Drug Benefits (ODB) which provides information on all prescriptions covered by the ODB (based on financial need for those under 65 years of age and universally for young people up to age 25); and the Registered Persons Database (RPDB) containing information on patient demographics and deaths. The Ontario Community Assessment of Need (OCAN) database captures all first episode patients attached to EPI programs in Ontario. OCAN will be used to develop a control population of FEP patients who are attached to non-NAVIGATE EPI programs. Statistics Canada estimates will be used to derive neighbourhood income and rurality. These data sources can be linked via the encrypted health card number such that all the information is available for each individual, and de-identified.

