Matched Controls: Each NAVIGATE subject will be matched to two types of subjects: 1) FEP patients attached to EPI programs who are not participating in the NAVIGATE trial; and 2) FEP patients with no EPI program attachment. Control cases will be matched to NAVIGATE subjects based on OCAN admission date for patients attached to EPI programs and at time of first diagnosis for those patients not attached to EPI programs. Patients with no EPI attachment will be identified using a validated algorithm that identifies all incident cases of psychotic disorders⁶⁹. The diagnostic codes vary by database and included ICD-9, ICD-10, DSM-IV codes. In order to be a FEP case among the non-EPI attached control group, subjects will not have had a non-affective psychotic disorder diagnosis within five years of the matching date. We will use propensity score matching to create the 2 comparison groups of non-NAVIGATE subjects. Propensity score matching mimics the characteristics of a randomized trial using observational data. A propensity score defined as the probability that a person is in the “exposed” category. In this case, the exposure condition is access to the NAVIGATE protocol. The propensity score is developed using logistic regression to model exposure to NAVIGATE as a function of observed covariates to yield a probability of NAVIGATE access for each subject. The propensity score model will include sociodemographic characteristics, clinical factors, and prior service use (defined below). We will match non-NAVIGATE to NAVIGATE subjects based on year of index diagnosis and caliper of the propensity score. Non-NAVIGATE Subjects will be assigned the same admission date as NAVIGATE subjects.

System Outcomes (Hospitalization, ED visits, suicide attempts): Our primary outcome is number of psychiatric hospitalization days in the year following NAVIGATE admission. We will include secondary outcomes, such as ED visits and suicide attempts. Hospitalization-based outcomes will include number of psychiatric hospitalizations and time to first psychiatric hospitalization. We will measure psychiatric emergency department visits with a year of admission as well as ED visits for suicide attempts. Visits to psychiatrists and primary care physicians will also be counted^{70,71}. Visits to primary care physicians will be stratified as mental health related versus non-mental health related based on a previously validated algorithm⁷².

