6.2. Benefits

Past studies have shown that implementation of a team-based model of first episode psychosis care demonstrated significant benefits compared to treatment as usual. This study may benefit participants in that it might help with patient engagement, and greater quality of life. Ontario research has shown that EPI programs in general are associated with more contact with outpatient psychiatry, fewer ED visits, and reduced mortality¹². The RAISE study found that the NAVIGATE intervention was associated with greater treatment retention, improvement in quality of life and psychopathology and involvement in work or school compared with standard community care²⁰. The benefits of this study include the long-term contribution to determine whether the NAVIGATE will lead to improved health outcomes for youth and emerging adults experiencing early psychosis. For the longitudinal assessments, there is a reasonable likelihood that quality of care delivered through NAVIGATE will be superior. Also the use of measurement to assess progress, symptoms and functioning over time has been associated with improved outcomes.

7. Innovation/Impact/KT/Future Plan

Building on Existing Structures: We established new relationships and built on existing ones over the past several months and years to set the stage for this project. Efforts and substantial investment of time with persons with lived experience, family members, front-line clinicians, members and leaders of invested organizations and networks within Ontario, and across Canada along with U.S. EPI and NAVIGATE leadership now position us uniquely to conduct the study.

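### Suicide attempts are measured only through ED visits, and the promised mortality outcome and time alive are not carried into the system-level analysis

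*Combined protocol and SAP*

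**What the plan says.** Objective 2 lists mortality and suicide attempts among the system-level outcomes, and the background text on ICES data does the same. Hypothesis 2 predicts "fewer days in hospital, fewer ED visits, fewer suicide attempts, lower mortality, and lower costs" for patients who receive NAVIGATE.

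The System Outcomes paragraph, under System Level Outcomes + Analytic Plan (Objective 2), turns these into measures. It states "Our primary outcome is number of psychiatric hospitalization days in the year following NAVIGATE admission", then "We will include secondary outcomes, such as ED visits and suicide attempts", and later "We will measure psychiatric emergency department visits with a year of admission as well as ED visits for suicide attempts". Mortality appears neither in that paragraph nor in its heading.

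The Statistical Analysis paragraph that follows models total hospital days by linear or Poisson regression according to their distribution, and secondary outcomes by logistic or Cox regression. It does not name mortality, has no term for time at risk, and gives no rule for patients who die within the year.

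The Data Sources paragraph already links NACRS for ED visits, CIHI-DAD and OMHRS for hospital stays, and "the Registered Persons Database (RPDB) containing information on patient demographics and deaths". It mentions deaths but not cause of death.

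**The concern.** An ED-only definition ties the attempt outcome to one route of care. A patient admitted directly after self-harm, or who self-harms during a stay, has no qualifying record. Neither has a person who dies without reaching an ED. The share missed may also differ between groups that use services differently, and that would bias the comparison.

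Mortality is promised in the objective and hypothesis but has no definition, window or model. It could therefore be left unreported, or analysed in a way chosen after the data are seen.

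A patient who dies stops accruing hospital days and visits, and fewer of each is the hypothesised benefit. The plan itself says that "associated mortality rates are 24 times greater in the 12 months after diagnosis compared to the general population", and this period is close to the outcome window. It also says that "EPI programs in general are associated with more contact with outpatient psychiatry, fewer ED visits, and reduced mortality". Unequal deaths are therefore most plausible in the comparison with patients who have no EPI contact.

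**Working it through.** The plan gives no event rate, effect size or power for the system-level outcomes, so it has no figure to reproduce. The first two steps compare texts. The last three use assumed rates, because the documents give none.

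**1. Each outcome followed through the plan**

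| Outcome | Objective 2 and hypothesis 2 | System Outcomes paragraph | Statistical Analysis paragraph |
|---|---|---|---|
| Hospital days | named | psychiatric days in one year | linear or Poisson, no time-alive term |
| ED visits | named | psychiatric visits in one year | general rule for secondary outcomes |
| Suicide attempts | named | ED visits for an attempt | general rule for secondary outcomes |
| Mortality | named | absent | absent |

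Costs have their own paragraph and model. Mortality is the only outcome of Objective 2 that is dropped between the objective and the definitions.

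**2. Which attempts count, as written**

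- Attempt seen in an ED, fatal or not: can be counted.
- Direct admission for self-harm: not counted as an attempt, although the stay enters hospital days if it is psychiatric.
- Self-harm during an admission: not counted as an attempt.
- Fatal attempt with no ED visit: not counted as an attempt. It would show only under mortality, which is undefined.

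**3. Attempts missed** (assumed risk *a*; assumed share *f* not seen in an ED; 400 patients as in the recruitment forecast)

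Captured events = 400 × *a* × (1 − *f*).

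- *a* = 5%: 20 events, of which 19 (*f* = 5%) down to 14 (*f* = 30%) are captured.
- *a* = 10%: 40 events, of which 38 down to 28 are captured.

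The observed ratio equals the true ratio × (1 − *f*₁)/(1 − *f*₂). If *f* is equal in both groups, only events are lost. If *f* is 10% in one group and 20% in the other, the factor is 0.90/0.80 = 1.125, or 0.80/0.90 = 0.89 the other way round.

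**4. Effect of deaths on mean hospital days** (assumed one-year death risk *m*, deaths spread evenly over the year)

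Mean time alive is 1 − *m*/2 years, so mean days are understated by about *m*/2.

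- *m* = 0.25% (1 death in 400): 0.125%.
- *m* = 1% (4 deaths): 0.5%.
- *m* = 3% (12 deaths): 1.5%, or 3% if every death fell at the start of the year.

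With equal true day rates, the apparent ratio of days is (1 − *m*₁/2)/(1 − *m*₂/2):

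- 3% versus 1%: 0.985/0.995 = 0.990.
- 1% versus 2%: 0.995/0.990 = 1.005.

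**5. What a mortality comparison could show** (400 versus 400, assuming 1:1 matching and ignoring the matching; two-sided 5% normal approximation for two proportions)

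| Assumed one-year risks | Power |
|---|---|
| 0.5% vs 1% | 13% |
| 1% vs 2% | 21% |
| 1% vs 3% | 52% |

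For the last row, the standard error is √(2 × 0.02 × 0.98/400) = 0.00990 under the null and √((0.0099 + 0.0291)/400) = 0.00987 under the alternative. Then z = (0.02 − 1.96 × 0.00990)/0.00987 = 0.06, and the power is 52%.

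**The case against.** The strongest reply is that the plan does intend to count deaths. Mortality is a named outcome in the objective, the hypothesis and the ICES background, the death registry is linked, and the secondary list is open-ended. This stands. A reader might infer that deaths enter no system outcome at all, and the documents do not support that. But an open list specifies no definition, window or model.

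A reader might also infer that in-hospital self-harm lowers the hospital-day count, or that death is rewarded enough to disguise harm. Neither follows. An inpatient who self-harms and survives goes on accruing days, and step 4 shows a shift of about 1% or less in the ratio of days. The mortality contrast in the background is between EPI and no EPI. It says nothing about NAVIGATE against other EPI programs. If deaths are more frequent without EPI, ignoring them lowers that group's count and so works against hypothesis 2.

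One can build an example in which counting fatal attempts moves a ratio from 1.00 to 0.90: 5% ED-treated attempts in both groups, plus 0.4% and 1.0% fatal, gives 5.4/6.0. Every rate in it is assumed, as is the premise that no fatal attempt reaches an ED. With 20 events in each group of 400, the standard error of the log ratio is √(2/20 − 2/400) = 0.308. The 95% interval is then 0.55 to 1.83, far wider than such a shift.

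Finally, the plan never says that ED visits are the sole source for attempts, and references 70 and 71 concern suicide and self-harm by title. They are attached to the sentence on physician visits, however, and no definition is taken from them in the text.

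**Conclusion.** The concern holds as a gap in definition and analysis. The only stated measure of a suicide attempt misses events recorded solely in hospital records and fatal attempts with no ED visit. Mortality is promised but not carried into the outcome or analysis paragraphs. The one-year counts take no account of time alive.

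The primary outcome is hardly affected: about 0.1% to 1.5% of mean days per group, for assumed death risks of 0.25% to 3% with deaths spread evenly over the year. The size of the loss for attempts cannot be fixed from the documents. For the assumed shares of 5% to 30%, it is 1 to 6 of every 20 events. The gain from a change lies in more complete ascertainment of attempts and in a mortality comparison that is actually specified. At this sample size, that comparison will be descriptive.

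**What to change.** In the System Outcomes and Statistical Analysis paragraphs:

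- Define a suicide attempt as an ED visit (NACRS) or a hospitalization record (CIHI-DAD or OMHRS) coded for self-harm within the year. Add suicide death only if cause of death can be linked.
- Do not use all-cause death as a component of the attempt outcome. It would mix in non-suicide deaths and count the same deaths under two outcomes.
- Report all-cause mortality from RPDB as a separate outcome for all three groups over the same one-year window, descriptively and with confidence intervals, because events will be few.
- Model hospital days and visit counts with log time alive as an offset. This needs a log-link count model, so the linear-regression option for days would need its own statement on time alive.
- In time to first psychiatric hospitalization, state whether death is a censoring or a competing event.

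The cost is a few sentences and a little more programming on sources already listed. The downside is some misclassification in inpatient self-harm coding, so the ED-only result could be shown alongside.

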ii). Institute for Clinical and Evaluative Sciences (ICES) Data: A Unique Opportunity to Evaluate System-Level Impact – Meeting the Mandate of the Innovative Clinical Trial (ICT): Using data from ICES, which captures all physician and hospital-provided insured services in Ontario, we will compare population-based outcomes (hospitalizations, emergency department visits, suicide attempts and mortality) with two comparison groups: 1) all EPI program FEP patients who have not been part of the NAVIGATE trial; and 2) all FEP patients who are not attached to EPI programs. All EPI programs in Ontario report their service utilization data through the Ontario Common Assessment of Need (OCAN) dataset (OCAN is linked to ICES data). While accuracy of data within OCAN is variable, we have confirmed that we can accurately ascertain the initiation date of all EPI patients by sex within Ontario through ICES linkage. The ability to link NAVIGATE's primary clinical and implementation data with ICES data, and the capacity to identify all FEP patients in Ontario (whether treated in EPI programs or not) allows for a meaningful, valid, and highly generalizable comparison of outcomes. The use of propensity score methods will address confounding associated with observational studies, and mimics some of the characteristics of a randomized controlled trial⁵¹. Since outcome data across all comparison groups are routinely collected by ICES, this dramatically reduces the time and cost of a randomized controlled trial (RCT) (thus fulfilling the ICT mandate), because the study does not require costly, extensive follow-up.

ICES has developed a costing macro that we have used to study health care costs among individuals in Ontario with schizophrenia⁵². The costing macro ensures that we have the capacity to determine costs associated with NAVIGATE relative to EPI usual care and no EPI care, a key implementation outcome. Cost estimation adds to the feasibility and policy-relevance of scaling up.

3. Statement of Objectives and Hypotheses

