iv) AFFORDABILITY System Outcome – Cost (i.e. Implementation Evaluation Outcome iv):

We will employ a costing algorithm developed in SAS®, and available at ICES⁷³, to estimate all direct patient-level health care costs incurred by the public third-party payer (Ontario Ministry of Health and Long-Term Care) across the three comparison groups. We will include costs of hospitalizations (both non-psychiatric and psychiatric); ED visits; physician services (i.e. primary care, psychiatry and other care) and diagnostics tests; outpatient prescription drugs for individuals covered under the provincial public drug insurance plan only (for individuals under 65 who receive social assistance and currently universally for individuals under age 25); home care; long-term care; and other care (this includes other ambulatory care, such as same-day surgery/procedures, cancer and dialysis clinic visits, and other hospital-based care, such as rehabilitation and complex continuing care). The costing methodology used in the algorithm will include a bottom-up/micro-costing approach to cost services at the individual level. This approach will make use of individual episodes of care or utilization in the health care system and attached prices (or costs or amounts paid) to each one. A top-down approach, which allocates corporate aggregate (i.e. institutional) costs to individual visits or cases/episodes of care, will be applied in cases where individual unit costs are not available (e.g. for institutional care settings). Assuming that all subjects will incur health care costs, we will use a generalized linear model with a gamma distribution and log link to model health care costs. Actual model parameters will be determined by the nature of the cost distributions.

Covariates: We will extract information on sociodemographic characteristics, including age, sex, neighborhood-level income quintile, and rurality of residence. Clinical covariates will include type of diagnosis (schizophrenia, schizoaffective disorder, etc.), source of index diagnosis (hospitalization, outpatient visit), and history of visits with alcohol- or substance-related diagnoses. We will also measure prior service use for mental disorders, including the number of prior visits for mental health reasons with the primary care physician, visits to psychiatrist, emergency department visits related to mental health and addiction conditions, and previous psychiatric hospitalizations.

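### The cost analysis promises all direct payer costs but names no item for non-physician EPI staff; unless its algorithm captures them, it cannot by itself show lower costs than no EPI

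*Combined protocol and SAP*

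**What the plan says.** The cost analysis is in Section 4, under the AFFORDABILITY heading. Its stated aim is "to estimate all direct patient-level health care costs incurred by the public third-party payer (Ontario Ministry of Health and Long-Term Care" for NAVIGATE patients and both control groups. The itemisation begins "We will include costs of hospitalizations (both non-psychiatric and psychiatric); ED visits; physician services" and goes on to diagnostic tests, drugs covered by the public plan, home care, long-term care and a residual class of other care. That residual class is described by example: "this includes other ambulatory care, such as same-day surgery/procedures, cancer and dialysis clinic visits, and other hospital-based care", the last illustrated by rehabilitation and complex continuing care. Where unit costs are missing, the fallback is "A top-down approach, which allocates corporate aggregate (i.e. institutional) costs to individual visits or cases/episodes of care".

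One comparator, in the Data Sources paragraph of Section 4, is "FEP patients with no EPI contact". The same paragraph gives OCAN a single purpose: "OCAN will be used to develop a control population of FEP patients who are attached to non-NAVIGATE EPI programs". Section 2.1 does say that "All EPI programs in Ontario report their service utilization data through the Ontario Common Assessment of Need (OCAN) dataset", but adds "While accuracy of data within OCAN is variable". Hypothesis 2 (Section 3.2) predicts lower costs for NAVIGATE. System costs are part of primary objective 2 (Section 3.1), and this cost outcome serves as the plan's affordability metric.

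**The concern.** Much of NAVIGATE is delivered by people who are not physicians. Section 2.1 names resiliency training, supported employment and education, and family education as components. Section 3.3 says site professionals provide case management alongside psychiatric care. Stage 2 of Section 4 allocates the non-medication roles among staff. Section 2.1 also says the province funds EPI programs, so this cost falls within the payer perspective that the analysis claims.

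If the algorithm prices only hospital, emergency, physician, drug and similar items, the comparison with no EPI would credit NAVIGATE with any hospital use it avoids and leave out the cost of the team that may have avoided it. A finding of lower costs would then describe a subset of services while being labelled as all direct payer costs. Section 2.1 links cost estimation to decisions on scaling up, and Section 7 says a Ministry team wants to turn findings into policy, so the label matters.

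**Working it through.** The documents give no cost figure, cost difference or power statement for this outcome, so there is no plan figure to reproduce. The check has two parts.

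**1. Is the staff cost named anywhere?**

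- *Listed items:* none names EPI program staff or a community mental health service.
- *ICES data (Section 2.1):* described as capturing insured services from physicians and hospitals.
- *Data Sources (Section 4):* OHIP covers physician billings, and OCAN is used to form a control group. The list names no source for home care or long-term care either, although both are to be costed. It is therefore not a complete guide to what the algorithm covers.
- *SURF (Section 3.3) and clinician contact notes (Section 4, Fidelity):* both could describe the work of these staff, but they are assigned to service use, fidelity and penetration, not to costing.
- *Residual other care and top-down allocation:* either might take in some hospital-based EPI cost. Neither mentions EPI.

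So no named item and no stated data use covers the cost, and whether the algorithm captures it is left open.

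**2. What would non-capture do to the comparison with no EPI?**

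Notation, per patient:
- m0 = mean listed cost with no EPI
- R = ratio of mean listed costs, NAVIGATE to no EPI (the quantity a gamma model with log link estimates)
- p = unpriced EPI program cost per NAVIGATE patient
- u0 = unpriced community services per no-EPI patient
- d = (p − u0)/m0, the net unpriced cost as a share of m0

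Listed-cost difference / m0 = R − 1.

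Full difference / m0 = (R·m0 + p − m0 − u0)/m0 = (R − 1) + d.

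The part left out is d, and the listed saving disappears at d = 1 − R. In money, break-even is (1 − R)·m0, which is the no-EPI mean minus the NAVIGATE mean listed cost.

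Every value of R and d below is an assumption. Entries are the full difference as a percentage of m0.

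| R | d = −10% | 0 | 5% | 10% | 20% | 30% | Break-even d |
|---|---|---|---|---|---|---|---|
| 0.95 | −15 | −5 | 0 | +5 | +15 | +25 | 5% |
| 0.90 | −20 | −10 | −5 | 0 | +10 | +20 | 10% |
| 0.80 | −30 | −20 | −15 | −10 | 0 | +10 | 20% |
| 0.70 | −40 | −30 | −25 | −20 | −10 | 0 | 30% |

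At R = 0.90 the full difference runs from −20% to +20%. The listed saving could be understated, right or reversed.

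**Against other EPI programs.** Staff cost arises in both groups. Set the comparator's listed mean to 100 and R to 0.90. With an assumed staff cost of 20 in each group, the full ratio is (90 + 20)/(100 + 20) = 0.917. With 25 against 15 it is (90 + 25)/(100 + 15) = 1.00. Only the difference in staff cost can remove the saving, so the problem partly cancels here.

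**The case against.** The strongest reply is that the algorithm is an established one, described in a cited source, and that its item list is open-ended. The residual class and the top-down clause could already contain some EPI cost, and the incomplete source list makes silence weak evidence of exclusion. This stands: the documents show an unsettled scope, not a proven omission.

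A reader might infer that the omission biases the result toward lower costs. The documents do not support that. They give no program cost and no figure for community services used by no-EPI patients, so d could take either sign. Nor is EPI cost strictly zero among these controls. Data Sources speaks of no EPI contact, but the Matched Controls paragraph selects on lack of attachment to a program, and OCAN accuracy is said to vary.

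It is also fair to say that the arithmetic is an identity that holds for any omitted item, and that the break-even figure is the listed-cost difference with its sign reversed. It shows what a full-cost claim would require; it does not estimate program cost.

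Section 2.1 notes that the original trial re-allocated existing resources without new clinical funding. That bears on NAVIGATE against other EPI programs. It does not make staff cost zero against no EPI.

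Finally, the item list already shows most of the scope. True, but the phrase that frames the outcome still claims all direct costs.

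**Conclusion.** The point holds in a limited form. The promise of all direct payer costs is not matched by any named item or stated data use for non-physician EPI staff. Unless the algorithm captures that cost, the comparison of NAVIGATE with no EPI does not measure all payer costs and cannot by itself establish lower costs or affordability.

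Neither the size nor the sign of what is left out can be found in the documents. The break-even values (5% to 30% of the no-EPI mean for assumed ratios of 0.95 to 0.70) show how the conclusion depends on it; they do not predict an error. It would also go too far to rule out any lower-cost conclusion: one limited to the priced services would be legitimate, and confirmed full capture would settle the matter.

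The reach is moderate. The concern bears mainly on one of two comparators, and the primary system outcome is psychiatric hospital days, not cost. It should be corrected before the cost analysis is run.

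**What to change.** - In the AFFORDABILITY paragraph of Section 4, state whether the costing algorithm captures non-physician EPI program cost. If it does so fully, one sentence resolves the point.
- If it does not, or does so only in part, describe the outcome as costs of the listed services and state the exclusion.
- In that case, limit any lower-cost conclusion against no EPI to the priced services.
- Report alongside it the break-even net program cost per patient (no-EPI mean minus NAVIGATE mean listed cost). Its 95% interval should carry the uncertainty in both means, for example from a bootstrap of matched sets. Give the time horizon too: the cost paragraph states none, and the one-year window elsewhere in Section 4 is given for hospital and emergency outcomes.
- Optionally, add a program-cost sensitivity analysis that leaves out physician and hospital costs already priced.

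All but the last item need no new data. The sensitivity analysis is harder: SURF and contact notes do not cover the control groups, OCAN accuracy varies, and no named source is stated to record community services used by no-EPI patients. The price is a narrower and possibly less favourable cost claim, and a little more analysis.
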